**Table 14.2.1.1.2: ACR20: Exploratory pairwise comparisons among the dose groups within each regimen**

Logistic regression model at each time point, modeling the responders. Factors in the model are: treatment, region, and previous use of biologics. Placebo won't be used, so can be omitted from the overall model.

Per time point, the table will present:

- Per group: difference in percentage responders versus the other GLPG0634 groups within the same regimen (q.d. or b.i.d.), together with a 95% confidence interval of this difference (as provided by SAS PROC FREQ).
- Per group: p-value for pairwise comparison versus the other GLPG0634 groups. These p-values will be presented both as uncorrected p-values, and are derived as contrasts within the overall logistic regression model. As this is a purely exploratory analysis, no adjustment for multiplicity will be performed.

The "raw" SAS PROC output must be provided in a statistical appendix listing.

The table will show:

- NRI in ITT and in per-protocol
- LOCF in ITT and in per-protocol
- observed-case in ITT (inferential statistics at Week 12 only).

Table to be created for the Week 12 interim analysis as well, cut off at Week 12. ITT only.

**Table 14.2.1.1.3: ACR20: Exploratory pairwise comparisons between regimens within each daily dose level**

Logistic regression model at each time point, modeling the responders. Factors in the model are: regimen, dose, regimen\*dose interaction, region, and previous use of biologics. Placebo

subjects will not be used in this model (as there is no q.d./b.i.d. regimen available for placebo). The regimen\*dose interaction will be removed from the final model when not significant at level 0.10 (two-sided type-III p-value). Regimen will have 2 categories: q.d. or b.i.d. Dose will have 3 categories, corresponding to the total daily dose: 50 mg/day, 100 mg/day, or 200 mg/day.

Per time point, the table will present:

- Per dose: difference in percentage responders of q.d. versus b.i.d. within the same dose level (50, 100 or 200 mg/day), together with a 95% confidence interval of this difference (as provided by SAS PROC FREQ).
- Per group: p-value for pairwise comparison of q.d. versus b.i.d. These p-values will be presented both as uncorrected p-values, and are derived as contrasts within the overall logistic regression model. As this is a purely exploratory analysis, no adjustment for multiplicity will be performed.

The “raw” SAS PROC output must be provided in a statistical appendix listing.

The table will show:

- NRI in ITT and in per-protocol
- LOCF in ITT and in per-protocol
- observed-case in ITT (inferential statistics at Week 12 only).

Table to be created for the Week 12 interim analysis as well, cut off at Week 12. ITT only.

**Table 14.2.1.1.4: ACR50: Summary with overall p-value and pairwise comparisons versus placebo**

Repeat table of the ACR20 table.

The table will show:

- NRI in ITT
- LOCF in ITT
- observed-case in ITT (descriptive at Week 12 + 24; inferential statistics at Week 12 only).

Table to be created for the Week 12 interim analysis as well, cut off at Week 12.

**Table 14.2.1.1.5: ACR50: Exploratory pairwise comparisons among the dose groups within each regimen**

Repeat table of the ACR20 table.

The table will show:

- NRI in ITT
- LOCF in ITT
- observed-case in ITT (inferential statistics at Week 12 only).

Table to be created for the Week 12 interim analysis as well, cut off at Week 12.

**Table 14.2.1.1.6: ACR50: Exploratory pairwise comparisons between regimens within each daily dose level**

Repeat table of the ACR20 table.

The table will show:

- NRI in ITT
- LOCF in ITT
- observed-case in ITT (inferential statistics at Week 12 only).

Table to be created for the Week 12 interim analysis as well, cut off at Week 12.

**Table 14.2.1.1.7: ACR70: Summary with overall p-value and pairwise comparisons versus placebo**

Repeat table of the ACR20 table.

The table will show:

- NRI in ITT
- LOCF in ITT
- observed-case in ITT (descriptive at Week 12 + 24; inferential statistics at Week 12 only).

Table to be created for the Week 12 interim analysis as well, cut off at Week 12.

**Table 14.2.1.1.8: ACR70: Exploratory pairwise comparisons among the dose groups within each regimen**

Repeat table of the ACR20 table.

The table will show:

- NRI in ITT
- LOCF in ITT
- observed-case in ITT (inferential statistics at Week 12 only).

Table to be created for the Week 12 interim analysis as well, cut off at Week 12.

**Table 14.2.1.1.9: ACR70: Exploratory pairwise comparisons between regimens within each daily dose level**

Repeat table of the ACR20 table.

The table will show:

- NRI in ITT
- LOCF in ITT
- observed-case in ITT (inferential statistics at Week 12 only).

Table to be created for the Week 12 interim analysis as well, cut off at Week 12.

**Table 14.2.1.1.10: ACR20 at Week 12: Tabulation versus baseline characteristics**

The table will show two methods of imputing missing values: LOCF and NRI.

Frequency tabulation of the ACR20 response rate at Week 12 per treatment group, split up according to the following baseline categories:

- Demographics:
  - Region (as used in the central randomization)
  - Country
  - Gender
  - Age categories:
    - < 45 ;
    - [45,65[ ;
    - [65,75[ ;
    - ≥ 75 years
  - BMI categories:
    - ≤ 18.5;
    - ] 18.5 , 25.0 ] ;
    - ] 25 , 30 [,
    - ≥ 30 kg/m^2
- Baseline disease characteristics:
  - Duration of RA:
    - < 1;
    - [ 1 , 2 [ ;
    - [ 2 , 5 [ ;
    - [ 5 , 10 [ ;
    - [ 10 , 20 [ ;
    - ≥ 20 years
  - Baseline CRP:
    - <0.7 x ULN;
    - [0.7,1.0] x ULN;
    - ]1.0,1.2[ x ULN;
    - ≥ 1.2 x ULN
  - Baseline TJC68: < 20, ≥ 20
  - Baseline SJC66: < 20, ≥ 20
  - Baseline DAS28(CRP): high, moderate, low, remission (see further section on DAS28 for the definition of these categories)
  - RF status
  - Anti-CCP status
  - Previous use of:
    - Biological (anti-TNF or other biological DMARD) yes/no,
    - anti-TNF yes/no,
    - other biological DMARD yes/no,
    - conventional DMARD yes/no,
    - NSAID yes/no,
    - steroid yes/no,

- analgesic yes/no,
- other RA medication yes/no.

Population: ITT.

Table to be created for the Week 12 interim analysis as well.

**Table 14.2.1.1.11: ACR20 at Week 12: Exploratory logistic regression model containing baseline characteristics**

The table will show two methods of imputing missing values: LOCF and NRI.

Logistic regression model of the ACR20 response at Week 12, with the following exploratory factors:

- Treatment group
- Demographics:
  - Region
  - Country
  - Gender
  - Age as continuous variable
  - BMI as continuous variable
- Baseline disease characteristics:
  - Duration of RA as continuous variable
  - Baseline CRP as continuous variable
  - Baseline TJC68 and SJC66 as continuous variables
  - Baseline DAS28(CRP) as continuous variable
  - RF status
  - anti-CCP status
  - Previous use of:
    - Biological (anti-TNF or other biological DMARD) yes/no,
    - anti-TNF yes/no,
    - other biological DMARD yes/no,
    - conventional DMARD yes/no,
    - NSAID yes/no,
    - steroid yes/no,
    - analgesic yes/no,
    - other RA medication yes/no.

All these factors will be tested using a stepwise selection approach. Significance level to enter the model: 0.10; significance level to stay in the model: 0.05. The treatment groups will always be kept in the model, even when not significant at level 0.05. The table will present only the final model with type-III p-value and odds ratio estimates. The “raw” SAS PROC output must be provided in a statistical appendix listing, and will contain all details on the model building steps.

Population: ITT.

**Table 14.2.1.1.12: ACR-N: Summary with overall p-value and pairwise comparisons versus placebo**

P-values are generated from an ANOVA model at each time point. Factors in the model are: treatment, region, and previous use of biologics.

Per time point, the table will present:

- Per group: sample regular statistics.
- Per group: difference in LS-means versus the placebo group (GLPG0634 minus placebo), together with a 95% confidence interval of this difference.
- Overall type-III p-value for “treatment”.
- Per group: p-value for pairwise comparison versus the placebo group, derived from contrasts within the overall model. These p-values will be presented both as uncorrected p-values as well as corrected for multiplicity according to Hommel’s closed-testing method (SAS PROC MULTTEST).

Frequency per time point (weeks 12 and 24 only), and per treatment group. ACR-N will be presented in the following categories:

<10,  
 [10,20[,  
 [20,30[,  
 [30,40[,  
 [40,50[,  
 [50,60[,  
 [60,70[,  
 [70,80[,  
 [80,90[,  
 [90,100].

The “raw” SAS PROC output must be provided in a statistical appendix listing.

The table will show:

- LOCF in ITT
- observed-case in ITT (descriptive at Week 12 + 24; inferential statistics at Week 12 only).

Table to be created for the Week 12 interim analysis as well, cut off at Week 12.

**Table 14.2.1.1.13: ACR-N: Exploratory pairwise comparisons among the dose groups within each regimen**

ANOVA model at each time point. Factors in the model are: treatment, region, and previous use of biologics. Placebo won’t be used, so can be omitted from the overall model.

Per time point, the table will present:

- Per group: difference in LS-means versus the other GLPG0634 groups within the same regimen (q.d. or b.i.d.), together with a 95% confidence interval of this difference.
- Per group: p-value for pairwise comparison versus the other GLPG0634 groups. These p-values will be presented both as uncorrected p-values, and are derived as contrasts within

the overall model. As this is a purely exploratory analysis, no adjustment for multiplicity will be performed.

The “raw” SAS PROC output must be provided in a statistical appendix listing.

The table will show:

- LOCF in ITT
- observed-case in ITT (inferential statistics at Week 12 only).

Table to be created for the Week 12 interim analysis as well, cut off at Week 12.

**Table 14.2.1.1.14: ACR-N: Exploratory pairwise comparisons between regimens within each daily dose level**

ANCOVA model at each time point. Factors in the model are: regimen, dose, regimen\*dose interaction, region, and previous use of biologics. Placebo subjects will not be used in this model (as there is no q.d./b.i.d. regimen available for placebo). The regimen\*dose interaction will be removed from the final model when not significant at level 0.10 (two-sided type-III p-value). Regimen will have 2 categories: q.d. or b.i.d. Dose will have 3 categories, corresponding to the total daily dose: 50 mg/day, 100 mg/day, or 200 mg/day.

Per time point, the table will present:

- Per dose: difference in LS-means of q.d. versus b.i.d. within the same dose level (50, 100 or 200 mg/day), together with a 95% confidence interval of this difference.
- Per group: p-value for pairwise comparison of q.d. versus b.i.d. These p-values will be presented both as uncorrected p-values, and are derived as contrasts within the overall model. As this is a purely exploratory analysis, no adjustment for multiplicity will be performed.

The “raw” SAS PROC output must be provided in a statistical appendix listing.

The table will show:

- LOCF in ITT
- observed-case in ITT (inferential statistics at Week 12 only).

Table to be created for the Week 12 interim analysis as well, cut off at Week 12.

**Table 14.2.1.1.15: Time to ACR20 response: Summary with overall p-value and pairwise comparisons versus placebo**

Descriptive statistics per treatment group.

Between-group comparison (overall and all pairwise comparisons versus placebo)

P-values are generated from a Cox proportional hazards regression model. Factors in the model are: treatment, region, and previous use of biologics.

The table will present:

- Per group: N (number of events, number of censored, number in total), mean (SE), median, quartiles.

- Overall type-III p-values for treatment, region and previous use of biologics.
- Per group: p-value for pairwise comparison versus the placebo group. These p-values will be corrected for multiplicity according to Hommel's closed-testing method as implemented in SAS PROC MULTTEST. The uncorrected p-values will also be presented.

A frequency table of the time-to-event in categories (Week 1, Week 2, Week 4, Week 8, Week 12, never) will also be presented.

The "raw" SAS PROC output must be provided in a statistical appendix listing.

Population: ITT.

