### **Methods of Analysis**

Efficacy data (ACR20, ACR50, ACR70, ACR-N, DAS28(CRP), EULAR response, and ACR/EULAR remission, and components of the ACR, CDAI and SDAI at each post-dosing visit) will be analyzed descriptively.

Between-group comparisons will be done for each dose group versus the placebo group. Hommel's closed-testing correction procedure (as implemented in SAS PROC MULTTEST) will be applied to adjust for multiplicity.

This study is not powered for any formal comparison among the dose groups, nor for comparisons between q.d. and b.i.d. regimens. However, differences between q.d. and b.i.d. regimens will be calculated and presented with a 95% confidence interval. Differences between q.d. and b.i.d. regimens will also be tested exploratively via a model containing the total daily dose (50/100/200 mg) as well as the regimen (q.d./b.i.d.). Differences among the q.d. groups and among the b.i.d. groups will be described in the same way. No adjustment for multiplicity will be done for these exploratory differences.

Nonresponding subjects from the placebo and lowest dose groups who are re-randomized at Week 12 will be handled as follows:

- Their Week 12 value will be carried forward in the original treatment group to all further time points (and between-group comparisons) after Week 12.
- Their actual assessments on Weeks 16, 20 and 24 will be analyzed descriptively as these represent their response after 12 weeks of GLPG0634 exposure after first having failed on placebo or a low dose.

Analysis methods per post-Baseline time point:

- Binary parameters: logistic regression model with factors treatment, region and previous use of biologics.
- Continuous parameters: changes from Baseline and percent changes from Baseline: using an analysis of (co)variance model with factors treatment, baseline value, region and previous use of biologics.
- Time to response (ACR20/50/70) will be analyzed using Kaplan-Meier survival techniques, and groups will be compared against placebo using a Cox proportional hazards regression model with factors treatment, region and previous use of biologics.

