### 1.4. FLOWCHART

Event	Screening	Baseline 	Treatment period 									FU visit 
			D8/ W1	D15/ W2	D29/ W4	D57/ W8	D85/ W12	D113/ W16	D141/ W20	D169/ W24	EDV 	
Informed consent	Written informed consent will be obtained before any study-related procedures and/or assessments are performed.											
Inclusion/ exclusion criteria	X	X 										
Demographic data and baseline disease characteristics	X											
Medical history/ concomitant illnesses	X											
Physical examination	X 	X					X			X	X	X
Serology 	X											
TB test and chest X-ray 	X											
Pregnancy test 	X	X	X	X	X	X	X	X	X	X	X	X
12-Lead ECG	X						X			X	X	X
Vital signs 	X	X	X	X	X	X	X	X	X	X	X	X
Clinical laboratory tests 	X	X	X	X	X	X	X	X	X	X	X	X
PK blood samples 					X		X			X	X	
PD blood samples 		X	X		X		X			X	X	

 Subjects will begin to take their treatment on the next morning (Day 1) following randomization.

 During the treatment period, a visit time window of ± 2 calendar days is allowed.

 Follow-up visit will be performed only for subjects discontinuing prematurely from the study and for subjects not entering the Long Term Follow-up study GLPG0634-CL-205.

 Early discontinuation visit.

 Eligibility criteria check based on the laboratory results from the Screening visit.

 At Screening, includes height and weight.

 Includes Hepatitis B and C, HIV 1 and 2, RF, and anti-CCP.

 X-ray should be performed if results from an X-ray performed in the previous 3 months are not available at the site.

 For female subjects only. To be performed on serum at Screening and Week 24/EDV and on urine for other visits.

 Vital signs are defined as blood pressure (systolic and diastolic), HR, and oral temperature.

 Refer to protocol Section 9.7.1.4.2..

 PK samples: 1 blood sample (2 mL) for analysis of GLPG0634 and its main metabolite (G254445) in plasma.

 PD samples: 4 blood samples (2x4 mL for serum preparation and 2x2.5 mL in PAXgene tubes) will be collected for analysis of serum (analytes and miRNA profiling) and whole blood (gene expression in circulating leukocytes, mRNA and miRNA profiling).

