### **5. SOFTWARE AND PROCEDURES**

#### **5.1. SOFTWARE**

SAS version 9.3 (or higher) will be used for programming.

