#### The time to ACR20 response

= (date of first time ACR20 response is reached) – (date of first medication intake) + 1 day, if the subject achieved ACR20 response during the initial 12 weeks treatment period, or  
= MIN (date of the Week 12 visit , date of trial termination) – (date of first medication intake) + 1 day, in case the subject did not achieve ACR20 response at any time during the initial 12 weeks treatment period.

Next to this, the visit during which the ACR20 response was first recorded will be analyzed as well:

- Week 1
- Week 2
- Week 4
- Week 8
- Week 12
- Never (i.e., subject did not achieve ACR20 response during the initial 12 weeks of treatment).

The time to ACR50 response and the time to ACR70 response are defined in the same way.

Note that the study period 2 cannot be used for the time-to-event derivation, because of the predefined potential treatment shifts at Week 12.

Note that if for a specific visit both the regular CRP as well as the high-sensitive CRP are available, the high-sensitive CRP will be used for the derivation of the percentage change from baseline and also for the ACR20/50/70/N.

Note that the percentage change from baseline remains missing if the baseline value itself equals zero.

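### Time to ACR20/50/70 response is tested by a Cox model on actual visit dates with no tie method named; if Breslow ties are used, power is lost, mainly for ACR20 (minor point, supportive analysis)

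*SAP*

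**What the plan says.** Protocol 8.8.1.3 (Methods of Analysis) sets the method for time to response: "groups will be compared against placebo using a Cox proportional hazards regression model with factors treatment, region and previous use of biologics". SAP 6.1.2.3 repeats it, and Table 14.2.1.1.15 implements it: "P-values are generated from a Cox proportional hazards regression model".

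SAP 8.1.1 counts the event time in days from first intake to the "date of first time ACR20 response is reached". Subjects without a response in the first 12 weeks are censored at "MIN (date of the Week 12 visit , date of trial termination"). Both are calendar dates, not planned visit days. For those dates, SAP 1.4 says: "During the treatment period, a visit time window of ± 2 calendar days is allowed".

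The same section adds that "the visit during which the ACR20 response was first recorded will be analyzed as well". In the results table that variable is only tabulated: "A frequency table of the time-to-event in categories (Week 1, Week 2, Week 4, Week 8, Week 12, never) will also be presented".

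On tie handling both documents are silent. SAP 5.1 names only the software: "SAS version 9.3 (or higher) will be used for programming".

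The table reports event counts, mean, median, quartiles, and uncorrected and Hommel-corrected p-values against placebo. It lists no hazard ratio; that would appear only in the raw output kept as an appendix.

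**The concern.** The true time of response lies somewhere between two visits. The plan treats the visit date as if it were that time, which has two consequences.

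First, ties are heavy. When many events share a day, the Breslow approximation pulls the treatment coefficient toward zero and the test loses power. Because the SAP leaves the tie method open, the result depends on whatever the program happens to use.

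Second, order within a window carries no information about speed of response. A non-responder seen on Day 83 leaves the risk set before a responder seen on Day 87 is counted, although both were assessed at the planned Week 12 visit.

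At stake is the sensitivity of the comparisons of speed of response between each of six regimens and placebo. The validity of any positive finding is not at stake.

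**Working it through.** **1. The plan's own power figures.** The documents give no power, hazard ratio or event count for time to response. Protocol 8.8.2 sizes the Week 12 ACR20 comparison with n = 85 per arm and alpha = 0.05/6 = 0.0083. Sidedness is not stated; two-sided is assumed, so z = 2.638. With pooled variance:

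power = Φ{[d√n − z√(2p̄q̄)] / √(p₁q₁ + p₂q₂)}

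For 20% vs 48%: (0.28 × 9.220 − 2.638 × 0.670) / 0.640 = 1.27, giving 89.8%. Likewise 40% vs 70% gives 91.3% (both stated as 90%), 20% vs 45% gives 80.9% and 40% vs 66% gives 78.4% (both stated as 80%). The design inputs are therefore read correctly.

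**2. How heavy the ties are.** Five visits × five allowed days = at most 25 distinct event days if visits stay in window. As an illustration, if 40% on placebo and 66% in each active arm respond, there are 34 + 6 × 56.1 ≈ 371 events, about 15 per day.

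**3. Simulation of the seven-arm design.** There were 1,200 trials per scenario, 85 per arm, with proportional hazards over the five visits, so HR = ln(1 − p₁)/ln(1 − p₀). For 40% vs 66% this is ln 0.34/ln 0.60 = 2.11. The ever-response rates, their split over visits and the date distributions are assumptions. Region and prior biologics were left out. Some fits gave convergence warnings, and fits that failed were dropped. Entries are power (%) per comparison at 0.0083. The three values in a cell are for all visits on the target day / 65% on it and the rest within 2 days / uniform within ±2 days.

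| Placebo vs active (true HR) | Cox, Breslow | Cox, Efron | Grouped-time | Loss with Breslow (points) |
|---|---|---|---|---|
| 40% vs 66% (2.11) | 75.2 / 78.2 / 79.9 | 82.1 / 81.2 / 81.4 | 82.2 | 7.0 / 4.0 / 2.3 |
| 50% vs 70% (1.74) | 42.8 / 48.2 / 50.7 | 53.8 / 52.3 / 53.3 | 53.8 | 11.0 / 5.6 / 3.1 |
| 60% vs 80% (1.76) | 52.8 / 60.1 / 63.2 | 67.4 / 66.7 / 66.1 | 67.6 | 14.8 / 7.5 / 4.4 |
| 15% vs 35%, ACR50-type | 59.7 / 60.9 / 61.3 | 62.6 / 62.4 / 62.5 | 62.6 | 2.9 / 1.7 / 1.3 |
| 7% vs 22%, ACR70-type | 48.1 / 49.1 / 49.7 | 50.0 / 50.3 / 50.3 | 50.1 | 2.0 / 1.0 / 0.4 |

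In the first three rows the median Breslow hazard ratio on target days is 2.01, 1.65 and 1.64, against true values of 2.11, 1.74 and 1.76.

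Two-arm runs (3,000 trials per scenario) over a wider range, placebo 20-60% and active 40-85%, give Breslow losses of 4 to 20, 2 to 10 and 1 to 8 points for the three date patterns. Efron on the same data loses about 0 to 1 point on target days and 0 to 4 with spread.

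**4. Different assumptions.** With HR 1.8 in every active arm, 8% dropout and 43% or 61% of placebo subjects ever responding, Breslow against grouped-time power is:
- uniform dates: 49.8 vs 53.9 (4.1 points) and 65.3 vs 71.7 (6.4);
- target days: 44.1 vs 53.8 (9.7) and 55.2 vs 71.5 (16.3).

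**5. Under Hommel.** Steps 3 and 4 use a fixed Bonferroni cut-off, whereas the plan uses Hommel. Rerunning the step 4 scenarios with Hommel-adjusted p < 0.05 (400 replicates) gives:
- spread dates: 63.0 vs 67.2 (4.2) and 80.3 vs 84.6 (4.3);
- target days: 56.5 vs 65.8 (9.3) and 73.7 vs 84.2 (10.5).

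Taking the protocol's design rates as ever-response rates, 40% vs 66% loses 3.0 points (spread) or 4.2 (target day), and 40% vs 70% loses 0.9 or 1.8.

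**6. Type I error.** With 50% responding in every arm and visits on target days, rejection at 0.0083 was 1.0% for Breslow and 1.3% for the other two (simulation standard error √(0.0083 × 0.9917/1200) = 0.26 points). At 0.05 the same null trials gave 4.6% against 6.4% (Efron) and 6.5% (grouped), standard error 0.63 points. Under the step 4 assumptions, null rejection at 0.0083 was 0.7 to 0.9% for all methods. Breslow errs toward caution.

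**The case against.** The strongest reply is that the documents never say Breslow. What they establish is an unspecified option, and under Efron the loss nearly disappears. That stands, and every Breslow figure here is conditional on it. The smaller scheduling effect does not depend on the tie method: with uniform dates, Efron still loses about 0.5 to 2.5 points in the seven-arm ACR20-type runs.

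Second, the largest losses need every visit on its exact target day and high response rates. The plan uses actual dates with a window, early-discontinuation and unscheduled visits can spread them further (SAP 3.3), and the planned test is Hommel. This also stands. The documented placebo rate of 20-40% applies to Week 12 alone, however. The rate of ever responding at any of five visits is at least as high, so the higher-rate rows are relevant.

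Third, the analysis carries little weight. Time to response is not among the listed secondary endpoints or objectives, is not powered, and is not in the interim list of SAP 6.2. Six of the nine tables are unadjusted exploratory contrasts. That limits the point to a minor one.

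A reader might infer that the Cox model is wrong and must be replaced, or that a double-digit loss applies to all three endpoints. The documents support neither. Cox is the protocol's method, Efron or exact ties make it adequate, and for ACR50 and ACR70 the loss is about 0 to 5 points. Nor would a shrunken hazard ratio appear in the planned tables, which list none.

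**Conclusion.** The point holds as a minor one. The documents show that response is seen at five visits, that actual dates are used as event and censoring times, that no tie method is stated, and that the matching grouped variable is derived but not tested.

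If Breslow ties are used, the loss at 0.0083 for ACR20-type rates is about 1 to 10 points with dates spread in the window and up to about 20 with all visits on target. Under Hommel the largest loss found was 10.5 points. These sizes rest on assumed response rates, timing and date patterns, and on models without region and prior biologics. The error is conservative, so no false claim of faster response would follow. The primary analysis, logistic regression of ACR20 at Week 12, is unaffected.

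**What to change.** In SAP 8.1.2, Tables 14.2.1.1.15 to 14.2.1.1.23, name the tie method: Efron, or the exact likelihood for tied continuous times. The discrete logistic version should not be used, because it estimates an odds ratio.

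Preferably, also use the visit of first response from SAP 8.1.1 as the time variable, with non-responders kept at risk through their last planned visit up to Week 12. This removes the scheduling order. It must be paired with Efron or exact ties, because collapsing dates to visits is the case in which Breslow loses most. An equivalent choice is binary regression with a complementary log-log link, one intercept per planned visit, and the same treatment, region and prior-biologic terms. The hazard ratio interpretation is unchanged, and the Kaplan-Meier plots can stay as they are.

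Naming the tie method costs one line and stays within the protocol's Cox model. Moving to the complementary log-log model also needs an entry in SAP Section 6.3 as a departure from the protocol. Neither needs new data.
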